## **8 TREATMENTS**

### **8.1 Study Treatment: Tofacitinib**

An investigational product, also known as investigational medicinal product in some regions, is defined as follows: A pharmaceutical form of an active substance or placebo being tested or used as a reference in a clinical study, including products already with a marketing authorization but used or assembled (formulated or packaged) in a way different from the authorized form, or used for an unauthorized indication, or when used to gain further information about the authorized form. In this protocol, the investigational product is tofacitinib.

Other medications used in the study as support or escape medication for preventative, diagnostic, or therapeutic reasons as components of a given standard of care are considered non-investigational products.

#### **8.1.1 Identification**

Tofacitinib is provided as 5 mg tofacitinib (equivalent to 8 mg tofacitinib citrate) tablets: White, round, immediate-release film-coated tablets, debossed with "Pfizer" on one side, and "JKI 5" on the other side.

### **8.1.2 Storage, Handling, and Dispensing**

The investigational product should be stored in a secure area according to local regulations. The investigator is responsible for ensuring that it is dispensed only to study subjects and only from official study sites by authorized personnel, as dictated by local regulations.

All investigational product supplies that will be used in the study must be maintained securely under the direct responsibility of the investigator or delegated by the investigator to the hospital pharmacist, or other personnel licensed to store and dispense drugs. All drugs shall be dispensed in accordance with the investigator's responsibility to ensure that an accurate record of drugs issued and returned is maintained.

The investigator is responsible for ensuring that the investigational product is stored under the appropriate environmental conditions (temperature, light, and humidity), as determined by the sponsor and defined by the Investigator Brochure or SmPC/ reference label. If concerns regarding the quality or appearance of the investigational product arise, do not dispense the investigational product and contact the sponsor immediately. Refer to the Investigator Brochure for additional information regarding handling, preparation, and storage of tofacitinib.

### **8.1.3 Additional Information for the Handling, Dispensing, and Storage of Tofacitinib**

White, round, immediate-release film-coated tablets, debossed with "Pfizer" on one side, and "JKI 5" on the other side, and available in:

Bottles of 28:	NDC 0069-1001-03
Bottles of 60:	NDC 0069-1001-01
Bottles of 180:	NDC 0069-1001-02

#### **Storage and Handling**

Store at 20°C to 25°C (68°F to 77°F). [See USP Controlled Room Temperature].  
Do not repackage.

### **8.2 Selection and Timing of Dose for Each Subject**

Patients will be treated with tofacitinib 5 mg to 10mg twice-daily. Treatment will be continued for up to 6 to 18 months to provide adequate time to assess the short-term efficacy and safety of tofacitinib in patients with alopecia areata. Study drug dose may be modified or held at the discretion of the investigator. Patients will then be followed for an additional 6 months after completion of treatment to assess the timing and incidence of relapse or to monitor for delayed or continued response after end of treatment.

### **8.2.1 Dose Modifications for Adverse Events**

If there is evidence of toxicity, as determined by laboratory tests or by clinical assessment that could place the subject at increased risk in the judgment of the investigator, administration of tofacitinib will be decreased or interrupted. Subjects may be considered eligible to continue with tofacitinib treatment only if full resolution of the adverse event is documented.

## **8.3 Concomitant Treatments**

### **8.3.1 Prohibited and/or Restricted Treatments**

The following medications are prohibited throughout the complete study period:

- Any medications known to affect hair growth in alopecia areata including but not limited to topical, intralesional or systemic steroids, anthralin, squaric acid, diphenylcyclopropenone, protopic, cyclosporine or any other medications which in the opinion of the investigator may affect hair growth in AA.
- Live vaccines.
- Use of any investigational drug other than study medication.
- Corticosteroid use at unstable dose and/or superior to the equivalent of prednisone 10 mg/day is not permitted.

### **8.3.2 Other Restrictions and Precautions**

## **8.4 Immunizations**

There is limited information available regarding the effectiveness of immunizations in non-human primates and humans that have been treated with tofacitinib. Limited data are available on the effect of therapeutic vaccinations in subjects receiving tofacitinib.

Due to the risk of infection, vaccination of subjects with any live vaccine is absolutely contraindicated during the treatment phase of the study (that is, at any time after entry into the induction period), as is the administration of LIVE oral polio vaccine to household contacts. The Centers for Disease Control and Prevention Advisory Committee on Immunization Practices (CDC-ACIP) recommends that subjects should not be administered a live virus vaccination for at least 3 months after discontinuing high-dose corticosteroid therapy (defined as more than 20 mg of prednisone per day for more than 2 weeks). In view of the long half-life of tofacitinib, study subjects should not be administered a live virus vaccine for a minimum of 3 months following the last dose of tofacitinib.

## **8.5 Treatment Compliance**

Compliance will be documented via the use of patient diaries to record the date and time of self-administration of medication at home. Study drug reconciliation will be performed at each visit during the treatment period.

## **9 STUDY ASSESSMENTS AND PROCEDURES**

### **9.1 Time and Events Schedule**

The Time and Events Schedule (Section 6, Table 3) summarizes the frequency and timing of various measurements.

#### Pre-screening procedures

Written informed consent will be obtained for this study by the principal investigator or his/her designee from all patients prior to any protocol-specific procedures. The study will be conducted in accordance with the Food and Drug Administration (FDA) approved revision of the Declaration of Helsinki, current FDA regulations, and International Conference on Harmonization (ICH) guidelines.

## Procedures Performed Prior to Treatment

### Screening (Day -28 to -1):

The following screening evaluations will be performed within 4 weeks prior to enrollment:

- Informed consent, inclusion/exclusion criteria, prior concomitant medications
- Medical history, physical examination, including a dermatological exam
- Vital signs, body weight
- Assessments of disease severity (amount of hair loss present) will be conducted including SALT (Severity of Alopecia Tool) and Physician's global assessment (PGA)
- Clinical laboratory evaluation (complete blood count, basic metabolic profile, hepatic panel and urinalysis), hepatitis B and C screening panel, HIV test, fasting lipid profile, serum pregnancy test for women of child bearing potential.
- Tuberculosis testing (PPD skin test or quantiferon test)

A visit will be scheduled 48-72 hours after placement of the PPD for reading of the test results. If the subject is unable to return for PPD, the results may be interpreted and documented by a qualified medical professional. If possible, the PPD reading visit may be combined with the baseline visit. The results of all assessments/tests listed above must be reviewed prior to enrollment to ensure that the patient meets entry criteria and that no exclusion criteria are present.

### Baseline (Day 0) Procedures Performed Prior to treatment

- Review of inclusion/exclusion criteria
- Vital signs, body weight
- Adverse events reporting, concomitant medication review
- Photography
- Physician evaluation utilizing the PGA and SALT scale
- Patient global assessment and quality of life assessment
- Urine pregnancy testing for WOCBP
- Blood collection for immunological studies
- Scalp biopsy (4mm punch biopsy)

### Weeks 4, 8, 12, 16, and 20 (Days 28, 56, 84, 112, and 140)

Visit days will have an acceptable window of  $\pm 3$  days.

- Vital signs, body weight
- Adverse events reporting, concomitant medication review
- Photography
- Physician evaluation utilizing the PGA and SALT scale
- Patient global assessment and quality of life assessment (week 12)
- Urine pregnancy testing for WOCBP
- Clinical laboratory evaluation (weeks 4, 8, 12, 16, and 20 weeks and as otherwise deemed necessary at the discretion of the investigator to monitor for abnormal values and for normalization of those values). In general, labs will be drawn ranging from weekly to every 4 weeks, depending on whether they are in or out of range, and to

monitor for resolution of abnormalities. Fasting lipid profiles will be repeated at months 1 and 2, end of treatment and as needed. Scalp biopsy (4mm punch biopsy) (week 4)

- Blood collection for immunological studies (week 4)
- Optional Scalp biopsy (4mm punch biopsy) in addition to weeks 4 and 24. Optional additional biopsies and blood draws may be obtained at the investigator's discretion and with the subject's permission as indicated by clinical considerations such as variation in the timeline to regrowth from one subject to another, focal apparent resistance to treatment, as well as other potential unpredictable clinical occurrences. Unscheduled biopsies and blood draws will ensure that tissue and blood samples can be obtained at optimal time-points to evaluate the changes occurring in response (or lack of response) to treatment. The patient will be given the option to agree to, or decline, the additional biopsies and blood draws.
- Optional Blood collection for immunological studies, at the discretion of the investigator as outlined above.

#### Week 24 (day 168±7) – End of Treatment

- Vital signs, body weight
- Physical and dermatological examination
- Adverse events reporting, concomitant medication review
- Photography
- Physician evaluation utilizing the PGA and SALT scale
- Patient global assessment and quality of life assessment
- Urine pregnancy testing for WOCBP
- Clinical laboratory evaluation
- Scalp biopsy (4mm punch biopsy)
- Blood collection for immunological studies

#### Weeks 28, 32, 36, 40, 44, 48, 52, 56, 60, 64, 68, and 72 (Optional Treatment Extension)

The treatment duration may be extended up to 12 additional months if clinically indicated at the discretion of the investigator. Visit days will have an acceptable window of ±7 days.

- Vital signs, body weight
- Adverse events reporting, concomitant medication review
- Photography
- Physician evaluation utilizing the PGA and SALT scale
- Patient global assessment and quality of life assessment
- Urine pregnancy testing for WOCBP
- Clinical laboratory evaluation (as scheduled and as otherwise deemed necessary at the discretion of the investigator to monitor for abnormal values and for normalization of those values).
- Optional Scalp biopsy (4mm punch biopsy). Optional additional biopsies and blood draws may be obtained at the investigator's discretion and with the subject's permission as indicated by clinical considerations such as variation in the timeline to regrowth from one subject to another, focal apparent resistance to treatment, as well as other potential

unpredictable clinical occurrences. Unscheduled biopsies and blood draws will ensure that tissue and blood samples can be obtained at optimal time-points to evaluate the changes occurring in response (or lack of response) to treatment. The patient will be given the option to agree to, or decline, the additional biopsies and blood draws.

- Optional Blood collection for immunological studies, at the discretion of the investigator as outlined above.

#### 8, 16, and 24 Weeks after End of Treatment – Observational Period

- Vital signs, body weight
- Physical and dermatological examination (only at End of Study)
- Adverse events reporting, concomitant medication review
- Photography
- Physician evaluation utilizing the PGA and SALT scale
- Patient global assessment and quality of life assessment (weeks 32 and 48)
- Clinical laboratory evaluation at 8 weeks after End of Treatment for safety parameters will be conducted if deemed necessary to assess for normalization of any previously abnormal values
- Optional Scalp biopsy as indicated
- Optional Blood collection as indicated

#### Early Termination

- Vital signs, body weight
- Physical and dermatological examination
- Adverse events reporting, concomitant medication review
- Photography
- Physician evaluation utilizing the PGA and SALT scale
- Patient global assessment and quality of life assessment
- Clinical laboratory evaluation if indicated
- Optional scalp biopsy and blood collection for immunological studies
- The reason for early withdrawal/study drug discontinuation must be documented

#### Unscheduled Visits

An unscheduled visit can occur at any time during the study. A source document must be maintained for these unscheduled visits. The date for the visit and any data generated must be recorded on the appropriate CRF. At treatment discontinuation/early termination subjects will undergo study evaluations per the Schedule of Assessments.

#### Duration of Treatment

Treatment will be continued for up to 6 to 18 months to provide adequate time to assess the short-term efficacy and safety of tofacitinib in patients with alopecia areata. Patients will then be followed for an additional 6 months to assess the timing and incidence of relapse of AA.

## **9.2 Study Completion or Early Discontinuation Visit**

At the time of study early withdrawal, the reason for early withdrawal and any new or continuing adverse events should be documented.

### **9.2.1 Study Drug Discontinuation**

If study drug administration is discontinued, the reason for discontinuation will be recorded.

**Table 3: Schedule of Assessments**

Visit	1 Screening	2 Base- line	3 Week 4	4 Week 8	5 Week 12	6 Week 16	7 Week 20	8 Week 24	± Weeks 28, 32, 36, 42, 44, 48, 52, 56, 60, 64, 68, 72	8W þ End of Tx	16W þ End of Tx	24W þ End of Tx
Day	-28 to -1	0	28±3	56±3	84±3	112 ±3	140 ±3	168 ±7				
Informed Consent	X											
Inclusion/Exclusion Criteria	X	X										
Medical History	X											
Body Weight	X	X	X	X	X	X	X	X	X	X	X	X
Physical Exam	X							X				X
Vital Signs	X	X	X	X	X	X	X	X	X	X	X	X
Concomitant Medications	X	X	X	X	X	X	X	X	X	X	X	X
Adverse events		X	X	X	X	X	X	X	X	X	X	X
Photography		X	X	X	X	X	X	X	X	X	X	X
SALT evaluation	X	X	X	X	X	X	X	X	X	X	X	X
Physician global assessment	X	X	X	X	X	X	X	X	X	X	X	X
Patient quality of life assessment, – DLQI & Skindex-29		X			X			X	X c	X		X
Patient global assessment		X			X			X	X c	X		X
Clinical laboratory evaluation*	X		X	X	X	X	X	X	X	X a		
Hepatitis & HIV testing	X											
Fasting Lipid Profile	X		X	X				X	X c			
PPD test and reading or quantiferon testing	X											
Serum pregnancy test	X											
Urine pregnancy test		X	X	X	X	X	X	X	X			
Scalp Biopsy		X	X	X b	X b	X b	X b	X	X b	X b	X b	X b
Phlebotomy for immunological studies		X	X	X b	X b	X b	X b	X	X b	X b	X b	X b

aClinical laboratory evaluation consists of CBC w/diff, BMP, hepatic panel, fasting lipid panel and urinalysis. Additional evaluations may be performed (including after the end of treatment visit) if needed to monitor or to verify normalization of previously abnormal lab values.

bOptional additional biopsies and blood draws may be obtained at the investigator's discretion and with the subject's permission as indicated by clinical considerations such as variation in the timeline to regrowth from one subject to another, focal apparent resistance to treatment, as well as other potential unpredictable clinical occurrences.

Unscheduled biopsies and blood draws will insure that tissue and blood samples can be obtained at optimal time points to evaluate the changes occurring in response (or lack of response) to treatment. The patient will be given the option to agree to, or decline, the additional biopsies and blood draws.

cat end of treatment

### **9.3 Study Materials**

Tofacitinib will be purchased at an approved commercial pharmacy and will be managed and dispensed by the Columbia University Research Pharmacy.

## **10 SAFETY ASSESSMENTS**

Analysis of safety is included as a secondary endpoint. All subjects who receive a dose of tofacitinib will be evaluated for safety. Safety outcomes include adverse events, clinically significant changes in vital signs, laboratory test abnormalities, and clinical tolerability of the drug. The investigator will determine the severity of each adverse event as mild, moderate, severe, or very severe. Laboratory findings that the investigator feels are clinically relevant should be recorded as adverse events. In addition, the investigator will determine the relationship of the adverse event to the administration of the study drug. Any occurrence of a SAE from time of consent forward, up to and including follow-up visits will be reported. See Section 6.5 for the SAE reporting procedures.

### **10.1 Physical Examinations**

During the treatment period, the physical examination is to be performed before administration of tofacitinib. While the interim physical examination may not be as comprehensive as the complete physical examination, important body systems should be included as deemed clinically indicated by the investigator. These body systems may include lymph nodes, liver, spleen, and breast. An interim physical examination may note any changes in the subject's condition since the last assessment and does not preclude examination of any of the body systems as clinically indicated.

### **10.2 Tuberculin Skin Testing**

A tuberculin skin test (PPD test: purified protein derivative tuberculosis skin test) should be performed and interpreted according to the applicable local Health Authority and/or Medical Society guidelines (those that provide recommendations for tuberculin skin testing for subjects who are to receive biologics, who are immunosuppressed, who have a prior history of BCG vaccinations(viii,ix), or who have a prior positive test). Tuberculin skin testing is not contraindicated for persons who have been vaccinated with BCG.

QuantiFERON® testing is an acceptable alternative when tuberculin skin testing is not appropriate. A tuberculin skin test is not required if one was performed within 1 month of screening and documentation of testing is on file. If tuberculin skin testing is performed at screening, then the 48-72-hour reading must be completed before administration of tofacitinib.

If the results of Tuberculin skin testing are equivocal or positive, quantiferon testing may be done to provide additional clinical information.

## 11 EFFICACY ASSESSMENT

### 11.1 Primary Efficacy Assessment

The study's *primary efficacy endpoint* will be the proportion of responders after 6 months of treatment, with response defined as 50% or greater hair re-growth from baseline as assessed by SALT score (Figure 6) at week 24. This is a relatively strict definition for defining responders and non-responders and was chosen to minimize the potential for spontaneous remission, in which approximately 8% or less are expected to achieve this magnitude of hair regrowth spontaneously.

#### SALT – Severity of Alopecia Tool

A. The proportion of scalp involvement is determined by dividing the scalp into 4 quadrants and estimating the percentage of the scalp surface that all the alopecic areas would occupy if placed together. The following groups will be used:

##### S: Scalp hair loss

S0 = No hair loss	S4 = 76%-99% hair loss
S1 = <25% hair loss	a = 76%-95% hair loss
S2 = 26%-50% hair loss	b = 96%-99% hair loss
S3 = 51%-75% hair loss	S5 = 100% hair loss

Percentage change from baseline (% regrowth) =

$$[(\text{SALT BL} - \text{SALT F/U}) / \text{SALT BL}] \times 100\% = \% \text{ change from baseline}$$

Absolute regrowth = SALT BL – SALT F/U = absolute change from BL

##### Body hair loss

B0 = No body hair loss

B1 = some body hair loss

[figure not shown]
B2 = total (100%) body hair loss

##### Nail involvement

[figure not shown]
N0 = No nail involvement

N1 = some nail dystrophy

N1a = 20 nail dystrophy

**Figure 6. SALT score.** The percentage of hair loss in any one of the four views (areas) of the scalp = the percentage hair loss x percent surface area of the scalp in that area. The SALT score then equals the sum of the scalp hair loss in each area.

### 11.1.1 Secondary Efficacy Assessments

As secondary endpoints, efficacy will be measured by changes in hair re-growth as a continuous variable as determined by physical exam and Canfield photography, as well as patient and physician global evaluation scores. To assess the durability of responses, patients will continue to be followed for an additional 6 months off treatment. To assess the durability of response and the incidence of relapse, patients who achieve 50% regrowth from baseline (50% reduction in baseline SALT score) will continue to be followed for an additional 6 months off treatment or until it is determined that relapse has occurred. Relapse will be defined as any recurrence of hair loss in responders (subjects achieving greater than 50% decrease in SALT score from baseline during the first 6 to 18 months of the study) who had achieved stable regrowth without continued loss for at least 2 months; and loss of  $\geq 25\%$  of regrowth in patients who had achieved 50% regrowth during treatment but still had chronic low grade hair loss. Nonresponders to 6 months study treatment (defined as failure to achieve 50% improvement in SALT score compared to baseline) will not be required to participate in the 6 month follow-up period but may be offered open-label tofacitinib if deemed appropriate by the investigator. Partial responders will continue to be followed to assess for delayed achievement of complete response. Analysis of safety is included as a secondary endpoint. All subjects who receive a dose of tofacitinib will be evaluated for safety.

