#### 8, 16, and 24 weeks after end of treatment (follow-up period off study medication)

All patients will be seen at 8, 16, and 24 weeks after completion of study drug, to determine durability of response or evidence for a delayed effect. Importantly patients who achieved  $\geq 50\%$  regrowth as measured by SALT score (responders) will be seen at 8, 16, and 24 weeks after end of study treatment in order to assess the frequency and timing of relapse or to capture the occurrence of further regrowth.

Relapse will be defined as any recurrence of hair loss in responders (subjects achieving greater than 50% decrease in SALT score from baseline during the first 6 to 18 months of the study) who had achieved stable regrowth without continued loss for at least 2 months; and loss of  $\geq 25\%$  of regrowth in patients who had achieved 50% regrowth during treatment but still had chronic low grade hair loss.

Nonresponders will also be offered the option to continue follow-up in order to assess for delayed response. Efficacy evaluations: SALT, PGA, Patient global assessment and patient quality of life assessment will be performed.

Blood draws for safety parameters will be conducted at 8 weeks after end of treatment if deemed necessary to assess normalization of any previously abnormal values.

Adverse events will be assessed at every visit.

Standardized photographs of the subject's scalp will be taken at every visit; blood draws for safety parameters and immune studies will be done based on the attached table of study procedures. Photographs will be used to support determination of percent hair regrowth. Photography will be performed using a high resolution digital camera with Intellistudio system from Canfield Scientific, Inc., Patients will be positioned using a laser guide, after which photographs of the entire scalp will be taken at standardized locations and at a fixed distance. Close-up photographs may also be taken using an epiluminescent attachment in order to assess for the presence of early regrowth.

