#### Duration of Treatment

After the screening period, subjects will begin tofacitinib 5mg twice-daily and will continue treatment for 6 months. The treatment may be extended by up to 12 additional months if clinically indicated at the discretion of the investigator.

The 18-month treatment period is expected to provide adequate time to assess the short-term efficacy and safety of tofacitinib in patients with moderate to severe AA, AT or AU. Responders will then be followed for 6 months off drug.

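### Conflicting rules on who attends off-drug follow-up, and no stated denominator, leave response and regrowth at 8, 16 and 24 weeks off drug open to outcome-related attendance

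*Combined protocol and SAP*

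**What the plan says.** The combined protocol and SAP gives four different rules for the six months off drug.

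- **Everyone.** Section 7.1, on the follow-up period: "All patients will be seen at 8, 16, and 24 weeks after completion of study drug". Section 8.2: "Patients will then be followed for an additional 6 months after completion of treatment". Section 9.1, Duration of Treatment: "Patients will then be followed for an additional 6 months to assess the timing and incidence of relapse of AA". The synopsis also follows patients in general, and Table 3 marks SALT at all three off-drug visits without restriction.
- **Nonresponders optional.** Later in the same part of section 7.1: "Nonresponders will also be offered the option to continue follow-up in order to assess for delayed response". Section 11.1.1 says that nonresponders to six months of treatment "will not be required to participate in the 6 month follow-up period but may be offered open-label tofacitinib".
- **Responders only.** Section 7.1, Duration of Treatment: "Responders will then be followed for 6 months off drug".
- **Responders until relapse.** Sections 5.1, 5.2 and 11.1.1 follow responders for six months or until relapse is determined. The definition of relapse begins "Relapse will be defined as any recurrence of hair loss in responders" and adds a second branch, loss of at least 25% of the regrowth, for responders with continuing low-grade loss.

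Section 11.1.1 also says: "Partial responders will continue to be followed to assess for delayed achievement of complete response". It does not define a partial responder, although it defines a nonresponder as anyone short of 50% improvement.

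The secondary outcomes in sections 5.2, 11.1.1 and 13.3 include percent regrowth (item 1), the 50% responder proportion compared with a historical rate below 10% (item 2) and the A5/SALT 25 proportion (item 3), each at 8, 16 and 24 weeks off drug. Section 13.2, headed as analysis populations, contains only accrual text. Section 13.4.3 plans descriptive proportions and means, without a denominator or a missed-visit rule. The only analysis set described is the one for safety.

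**The concern.** Under some of these rules a subject's presence at an off-drug visit depends on that subject's hair. Failure to respond can make attendance optional, and relapse can end it. Missing visits would then be related to outcome by design rather than by chance.

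If the analyst divides by those who attend, the off-drug proportion and mean describe a selected group, and with 15 subjects a few absences move them a long way. Readers could mistake an attendance effect for durability. Section 13.4.3 intends these summaries to guide later trials, so the error would carry forward.

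**Working it through.** **The plan's own figure.** No figure is given for the off-drug outcomes. The nearest is the power statement in section 13.1 (n = 15, 10% against 48%, type I error 5%). By the exact binomial test, rejection at 5/15 or more has a type I error of 0.0127 and power of 92.0%, so the stated value above 80% is confirmed. It is not in dispute here.

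**Inputs from the documents.** 15 subjects (synopsis, section 13.1); response as at least 50% regrowth (sections 5.1, 13.3); regrowth = (baseline SALT − follow-up SALT) / baseline SALT × 100% (section 11.1); SALT at each off-drug visit (section 9.1, Table 3).

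**Assumptions.** The documents give no attendance or relapse rates, so all counts below are assumed. At end of treatment 7 of 15 respond (47%, close to the planning value of 48%) and 8 do not. Four of the 8 nonresponders attend off drug and 4 do not. Intervals are exact (Clopper-Pearson) 95%.

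**Case 1: three responders fall below 50%, found at week 8.** Four responses are retained.

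| Basis | Count | Proportion (95% CI) |
|---|---|---|
| All treated, any visit | 4/15 | 27% (8–55%) |
| Attendees, week 8 (7 + 4, relapsers scored there) | 4/11 | 36% (11–69%) |
| Attendees, weeks 16 and 24 (three relapsers gone) | 4/8 | 50% (16–84%) |

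The ratio of the last row to the first is 0.500/0.267 = 1.9. A relapse found at a visit is scored at that visit. The exposed visits are therefore the later ones, and any visit that follows a relapse determined between visits, for example by the monthly calls in section 7.1.

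**Dependence on the undefined term.** The 4 attending nonresponders may come by choice or because they count as partial responders. If partial responders instead means subjects at 50% or more without complete regrowth, none of the 8 need attend. With none attending, the figures become 4/7 = 57% at week 8 and 4/4 = 100% later.

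**Case 2: the opposite direction.** A relapse can still be a response. After loss of a quarter of regrowth R, 0.75R remains, which is at least 50% whenever R ≥ 66.7%. For example, with baseline SALT 80 and end-of-treatment SALT 8, regrowth is 90%. Losing a quarter of the 72 points (18) gives SALT 26, and (80 − 26)/80 = 67.5%. Suppose 4 of the 7 responders relapse in this way at week 8 and leave, while all 8 nonresponders attend. Later visits then give 3/11 = 27% (6–61%) of attendees against 7/15 = 47% (21–73%) of all treated.

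**Mean regrowth.** Assume 80% in 7 responders, 30% in the 4 attending nonresponders, and x in the 4 absent.

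- Attendees: (7×80 + 4×30)/11 = 680/11 = 62%.
- All treated: (680 + 4x)/15, which is 53% at x = 30 and 45% at x = 0.
- Zero is not a lower limit. A subject going from SALT 40 to 80 has (40 − 80)/40 = −100%. With x = −100 the mean is 280/15 = 19%.

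**Range for missing subjects (case 1, weeks 16 and 24).** Four are in response, 4 are seen below 50%, and 7 are missing. The mechanical range is 4/15 = 27% to 11/15 = 73%. Three of the 7 missing were already seen below 50% at week 8. If only the 4 never seen are allowed as possible delayed responders, the upper end is 8/15 = 53%.

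**The case against.** The best defence is that this is a 15-subject open-label pilot with descriptive secondary summaries. Most passages and Table 3 do bring everyone back, and the experimental group named in item 2 could be read as all 15. Reporting the number assessed would also repair much of the problem at analysis. Sections 7.1 and 9.1 provide evaluations at early termination or discontinuation (including SALT in section 9.1), and section 7.1 allows an unscheduled visit after a telephone contact.

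These points limit the harm but do not remove it. No passage says which attendance rule prevails or how an absent subject counts. The extra evaluations reduce data loss without replacing SALT at the three fixed times.

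Several stronger readings are tempting but not supported:

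- *Attendance decides whether response beats the historical rate.* Every proportion above is at least 27%. Only an interval or test result crosses 10% (exact one-sided p = 0.056 for 4/15 and 0.005 for 4/8), and the plan specifies neither for these outcomes.
- *The bias is upward.* No attendance rates are given, and case 2 runs downward.
- *The primary endpoint is compromised.* It is measured at end of treatment, before off-drug attendance begins. The absence of an efficacy denominator there is a separate matter.
- *Nonresponders will be on drug at the off-drug visits.* The open-label offer may mean the optional treatment extension; the text does not say.
- *The relapse outcome is lost when follow-up ends at relapse.* The event itself is still recorded. However, item 7 refers to responders followed for six months, and a literal reader could exclude those who left early, so it needs a clarifying line.

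**Conclusion.** The concern holds as a conflict between attendance rules combined with a missing denominator. Because some of those rules tie attendance to response or relapse, an attendees-only summary of the planned off-drug outcomes can be biased in either direction. In the main illustration, identical hair outcomes read as 27%, 36% or 50%. This size rests on assumed counts and on one reading of an undefined term; the direction in the actual trial cannot be predicted. The consequence is for interpretation of durability and for later trial design, so the text should be corrected, but the trial's main conclusion does not depend on it.

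**What to change.** 1. **Attendance.** Reconcile sections 5.1, 5.2, 7.1, 8.2, 9.1 and 11.1.1 into one rule. All treated subjects who still consent, and for whom visits are judged appropriate, are asked to attend the three SALT visits already in Table 3, irrespective of response or relapse. Define partial responder or drop the term.
2. **Binary off-drug outcomes (50% response and A5/SALT 25).** Use all treated subjects as the denominator. Score attendees, including relapsers, by observed SALT. Count missing or re-treated subjects as not in off-drug response. Add a best/worst-case range as a sensitivity analysis, stating how subjects already seen below 50% are handled.
3. **Mean regrowth.** Report the number assessed at each visit, label the observed mean as attendees only, and add an all-treated sensitivity analysis that permits negative regrowth. Do not present zero regrowth as a bound.
4. **Item 7.** State that it includes responders whose follow-up ended at relapse.
5. **Related text.** The protocol team should reconcile the passages on open-label drug, extension, treatment duration and end-of-study timing. No clinical rule or duration is proposed here.

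The cost is an amendment with IRB approval (section 14.1), possibly re-consent, and some more attendance at visits already scheduled. The durability figure may be less favourable. Counting missing subjects as not in response can understate delayed response, which is why the range is reported beside it.
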